[Part 2 of 2 of the document. The other parts are not shown.]

The purpose of this statistical analysis plan (SAP) is to provide all information that is necessary to perform the required statistical analysis of the dose escalation (combination therapy) module (Part B) of study ONC001. It also describes the summary tables, figures and listings (TFLs) to be generated for Part B according to:

Protocol amendment 6, dated 26 June 2023;

Electronic case report form (eCRF) (Clinical Data Management System [CDMS] postproduction change [CPPC] #14, version 23.0, dated 14 April 2023);

UCB's standards for TFL shells version 2023Q1;

Part A TFL shells, final version 2.4, dated 04 July 2023;

Part B and C Mocks draft version 1.4, dated 4 September 2023 (under development);

Part A, B and C List of TFLs (LoT) draft version 1.2, dated 04 July 2023 (under development);

UCB's Derivation of Efficacy Endpoints document, version 0.6, dated 21 January 2022.

Unless specified in the sections below, Part B of the study will be analyzed as described in the most recent version of the protocol. If a future protocol amendment necessitates a substantial change to the analysis of the Part B study data, this SAP will be amended accordingly. In addition, if the methodology for the analysis of key study endpoints must be modified or updated prior to the final database lock for Part B of this study, a SAP amendment will be required. Protocol amendments that do not affect the statistical analysis will not necessitate an amendment to the SAP. If, after database lock, additional analyses are required to supplement the planned analyses described in this SAP, these changes will be described in the clinical study report (CSR) together with the associated rationale.

Note that there may be a number of data cut-offs defined prior to the final database lock for Part B due to the regulatory safety reporting requirements for this study.

The content of this SAP is compatible with the International Council for Harmonization (ICH)/Food and Drug Administration (FDA) E9 Guidance (ICH-E9).

UCB is the Sponsor and ICON PLC is the contract research organization (CRO) for this study.

2. PROTOCOL SUMMARY

2.1 Study objectives

2.1.1 Primary objective

The primary objective of Part B (dose escalation module) of this study is to characterize the safety profile of UCB6114 administered in combination with a trifluridine/tipiracil (TFD/TPI) standard of care (SoC) regimen in participants with locally advanced or metastatic colorectal adenocarcinoma, gastric adenocarcinoma, or adenocarcinoma of the gastroesophageal junction.

2.1.2 Secondary objective

The secondary objective of Part B of this study is to characterize the pharmacokinetics (PK) of UCB6114 administered in combination with a TFD/TPI SoC regimen in participants with locally advanced or metastatic colorectal adenocarcinoma, gastric adenocarcinoma, or adenocarcinoma of the gastroesophageal junction.

2.1.3 Exploratory/Tertiary objectives

The exploratory/tertiary objectives of Part B of this study are:

- To document any antitumor activity observed with UCB6114 administered in combination with a TFD/TPI SoC regimen according to relevant Response Evaluation Criteria in Solid Tumors (RECIST) criteria;
- To explore pharmacodynamics (PD) biomarkers of UCB6114 administered in combination with a TFD/TPI SoC regimen;
- To evaluate the immunogenicity of UCB6114 administered in combination with a TFD/TPI SoC regimen.

2.2 Study endpoints

2.2.1 Safety endpoints

2.2.1.1 Primary safety endpoints

The primary safety endpoints for Part B of this study are the incidence and severity of treatment-emergent adverse events (TEAEs) (including serious adverse events [SAEs]) from the first dose of UCB6114 on Day 1 of Cycle 1 to the Safety Follow-up (SFU) visit, and the incidence of dose limiting toxicities (DLTs) from the first dose of UCB6114 on Day 1 of Cycle 1 to the end of the DLT Observation Period (Day 28 of Cycle 1).

2.2.1.2 Other safety endpoints

The following other safety data will be assessed during Part B of the study to further support the characterization of the safety profile of UCB6114 administered in combination with a TFD/TPI SoC regimen.

- Clinical laboratory data (hematology, serum chemistry, coagulation and urinalysis);
- Vital signs (systolic and diastolic blood pressure, pulse rate, respiratory rate, and body temperature);
- 12-lead electrocardiogram (ECG);
- Echocardiogram (left ventricular ejection fraction [LVEF]);
- Eastern Cooperative Oncology Group (ECOG) performance status;
- Physical examination.

2.2.2 Pharmacokinetic and pharmacodynamic endpoints

2.2.2.1 Secondary pharmacokinetic endpoint

The secondary PK endpoint in Part B is the UCB6114 concentration by scheduled assessment for each UCB6114 dose level.

2.2.2.2 Exploratory pharmacokinetic endpoints

██████████ will be exploratory PK endpoints in Part B.

2.2.2.3 Exploratory pharmacodynamic endpoints

The following PD endpoints will be assessed in Part B and reported separately outside of the CSR:

- Change in protein marker levels in blood by scheduled assessment and UCB6114 dose level;
- Change in circulating tumor deoxyribonucleic acid (ctDNA) levels in blood by scheduled assessment and UCB6114 dose level.

2.2.2.4 Exploratory immunogenicity endpoints

Immunogenicity in Part B will be explored using anti-drug (UCB6114) antibody (ADA) sample status and participant classification, and changes in titer over time. Potential relationships between ADA and PK, PD, anti-tumor activity and safety may also be explored but these analyses will be reported separately outside of the CSR.

2.2.3 Efficacy endpoints

2.2.3.1 Exploratory antitumor activity endpoints

Antitumor activity in Part B will be explored using the following endpoints:

- Objective tumor response rate (ORR);
- Disease control rate (DCR);
- Duration of antitumor response (DOR);
- Progression-free survival (PFS);
- Overall survival (OS).

2.2.3.2 Other exploratory efficacy endpoint

To further explore efficacy in Part B of the study, changes from Baseline in the ECOG performance status scale will be assessed.

2.3 Study design and conduct

Study ONC001 is a multicenter, nonrandomized, open-label, Phase 1/2 study evaluating the safety, PK, efficacy (as assessed by antitumor activity), PD, biomarkers, and immunogenicity (ADA activity) of intravenous (iv) UCB6114 as monotherapy and in combination with selected SoC regimens in study participants with advanced solid tumors.

The study has a modular design including up to 3 dose escalation modules (Parts A, B, and C), 1 dose adaptation module (Part A1), and up to 4 dose expansion modules (Parts D, E, F, and G). Depending on emerging data, not all modules may open. This SAP is focused only on the

ascending dose escalation module of the study evaluating UCB6114 in combination with a TFD/TPI SoC regimen (Part B).

Part B consists of a Screening Period (28 days), a Treatment Period (consisting of 28-day cycles), a SFU visit (approximately 30 days after the last dose of study treatment), and a Final Visit (approximately 3 months after the last dose of study treatment).

In Part B, eligible participants with unresectable locally advanced or metastatic colorectal adenocarcinoma, gastric adenocarcinoma, or adenocarcinoma of the gastroesophageal junction will receive UCB6114 as an iv infusion in combination with orally administered TFD/TPI. The starting dose and schedule of UCB6114 will depend on the dose level evaluated in Cohort 3 of Part A (anticipated to be 500mg every 2 weeks [Q2W] iv), the emerging safety profile of UCB6114 monotherapy, and any predicted overlapping toxicities with TFD/TPI. Up to 3 UCB6114 dose levels (anticipated to be 500mg, 1000mg, and 2000mg administered Q2W iv) will be explored and up to 27 participants may be enrolled. Dose escalation decisions in this module will be guided by a model-based estimation of the probability of DLT in Cycle 1.

Part B will be undertaken using the modified toxicity probability interval (mTPI) method. The mTPI design uses a Bayesian decision framework to inform dose-escalation and dose de-escalation decisions. A target DLT rate of 25% with an equivalence interval (20% to 30%) will be used to estimate the maximum tolerated dose (MTD) of the combination regimen during dose escalation. For all UCB6114 dose levels, enrolled participants will be treated in cohorts of 2 to 4 participants (target of 3), who can be treated in parallel. Each UCB6114 dose level may have more than one cohort and will have a minimum of 3 and a maximum of 9 evaluable participants. For further detail on the mTPI method, the calculated model-based dose-escalation/dose de-escalation decisions to help inform the Safety Monitoring Committee (SMC)'s decision, and the determination of the MTD, please refer to Section 4.1.3.2.2 of the protocol. Detail on the operating characteristics for the mTPI design is included in [Section 2.4](#) below.

[figure not shown]
The planned duration of study treatment during Part B is 2 cycles. Participants may remain on study for additional cycles if they are receiving therapeutic benefit or until they fulfill one of the criteria for study discontinuation. Participants will continue treatment until disease progression, unmanageable toxicity, or withdrawal of consent. Upon discontinuation of treatment, participants will be referred to appropriate follow-up care per the investigator's judgment.

From Part B, a recommended Phase 2 dose for UCB6114 in combination with TFD/TPI (RP2D-T) will be determined based upon the totality of information, including the safety profile, PK data, PD biomarker data, and available antitumor activity.

Part B of the study is planned to be conducted at study sites in the United Kingdom (UK) and United States (US).

A schematic diagram of Part B of the study is provided in [Figure 2-1](#).

Figure 2-1: Study Schematic for Part B

bid=twice daily; D=Day; DLT=dose-limiting toxicity; iv=intravenous; mTPI= modified toxicity probability interval; po=oral; TFD/TPI=trifluridine/tipiracil

*Dose must not exceed 80mg/dose

Notes: A dose may be given in more than 1 cohort

Escalation to the next dose level or de-escalation to the previous dose level will be guided by the mTPI algorithm.

A Study Steering Committee (SSC) will be implemented prior to the start of Part B. In consultation with the SMC, the SSC will recommend to the Sponsor the dose and dosing regimen to be taken forward for Part B. Part B of ONC001 is planned to be initiated after Cohort 3 of Part A has completed the 28-day DLT assessment period, after consultation with the SMC, and when the SCC has provided a recommendation to dose escalate to the next protocol-defined level in Part A of the study. The SSC members will include the coordinating investigator, supporting co-investigators, and clinical experts not involved in the study. The medical, scientific, and clinical study expertise of the SSC will assist the Sponsor in identifying and resolving any study related issues, such as study design, study implementation and conduct, and data analysis and reporting.

During the Treatment Period, UCB6114 will be administered as an iv infusion Q2W, while TFD/TPI will be administered orally twice daily (bid) within 1 hour of completion of morning and evening meals at home on Days 1 to 5 and Days 8 to 12 of each 28-day cycle. For the convenience of the participants, TFD/TPI can be administered at home to allow for the 12-hour interval between TFD/TPI doses associated with meals. The starting dose of TFD/TPI in adults is 35mg/m² administered orally bid (total daily dose of 70mg/m²) with dosage calculated for each participant according to body surface area (BSA) (see Table 4-4 of the protocol). The dosage must not exceed 80mg/m² (based on the trifluridine component).

It is expected that up to 3 dose levels of UCB6114 will be explored in combination with the standard TFD/TPI dosing regimen. However, additional dose levels may be added based on emerging data and recommendations of the SMC. Dose escalation steps are currently planned at a maximum of 2-fold. Escalating dose levels in Part B will not exceed a dose level tested and considered safe by the SMC to allow dose escalation in monotherapy (Part A).

Eligible participants who withdraw from the study before receiving study treatment will be replaced. Participants who fail to receive the second planned dose of UCB6114 within 7 days of

the scheduled administration day during the 28-day DLT Observation Period for reasons not related to toxicity will be replaced by a new participant in that cohort. Safety data for replaced participants will be included in the data listings and in the summary tables, as applicable.

2.4 Determination of sample size

No formal statistical sample size calculation has been performed for the dose escalation modules in study ONC001.

The number of participants likely to be enrolled in Part B depends on how many dose levels are needed to define the RP2D-T for combination therapy. In Part B, up to 27 eligible participants will be enrolled. It is expected that up to 3 dose levels of UCB6114 will be explored in combination with the TFD/TPI dosing regimen, respectively. However, additional dose levels may be added based on emerging data and recommendations of the SMC.

Between 3 and 9 participants are expected to be enrolled at each dose level of UCB6114 depending on the observed toxicity/observation of DLTs. An administrative decision to stop enrolling into Part B may be made by the Sponsor at any time. “Dose level” refers to a particular UCB6114 dose, that can be given to one or more cohorts, not necessarily consecutively.

The operating characteristics of the mTPI design were evaluated using a simulation approach under four scenarios (see Table 2-1) and based on no DLTs observed in the first 2 cohorts in Part A monotherapy treatment (UCB6114 100mg and 250mg). The results of this evaluation can be seen in Table 2-2.

Table 2-1: Scenarios used for evaluating the operating characteristics of the mTPI design. Orange cells indicate the correct decision assuming a maximum tolerated toxicity of 25% (equivalence limits 20%, 30%)

UCB6114 Dose	Probability of a DLT			
	Scenario 1	Scenario 2	Scenario 3	Scenario 4
Dose 1 (500 mg)	0.05	0.05	0.15	0.25
Dose 2 (1000 mg)	0.05	0.15	0.25	0.35
Dose 3 (2000 mg)	0.05	0.25	0.35	0.50

Table 2–2: Evaluation of the operating characteristics of the mTPI design with a target maximum tolerated toxicity of 25%, using 5000 simulated trials for each scenario. Orange cells indicate the correct decision.

Final UCB6114 Dose Selected	Scenario 1	Scenario 2	Scenario 3	Scenario 4
	% of Simulations (Number of Simulations)			
Dose 1 (500 mg)	3.9% (196)	5.2% (262)	31.6% (1580)	53.3% (2666)
Dose 2 (1000 mg)	3.9% (195)	35.1% (1755)	40% (1999)	26.7% (1337)
Dose 3 (2000 mg)	91.4% (4571)	58.9% (2947)	21.6% (1080)	3.8% (191)
Overly Toxic at First Cohort	0.8% (38)	0.7% (36)	6.7% (336)	15.2% (758)
Overly Toxic after First Cohort	0	0	0.1% (5)	1% (48)

3. DATA ANALYSIS CONSIDERATIONS

3.1 General presentation of summaries and analyses

All TFLs will be produced by ICON PLC using SAS® Version 9.4 or higher (SAS Institute, Cary, North Carolina, USA). ICON PLC will also produce the analysis datasets which will adhere to the Clinical Data Interchange Standards Consortium (CDISC) guidance documents for Analysis Data Model (ADaM) and follow the Sponsor's interpretation. General statistical and reporting conventions will follow the current UCB Global Conventions Document Version 1.1.

Data will be summarized by UCB6114 dose level (treatment group), visit and timepoint, as applicable. All relevant reported and derived data will be listed and will be presented by treatment group, study participant and visit, as applicable.

Categorical variables will be summarized using frequency counts and percentages. Unless otherwise stated, the denominator for the percentages will be based on the number of participants in the respective analysis set, treatment group, visit and timepoint (as applicable) with non-missing data.

When reporting frequency counts and percentages, the following rules apply:

- For categories where all participants fulfill certain criteria, the percentage value will be displayed as 100;
- For categories where zero participants fulfill certain criteria, there will be no percentage displayed;
- All other percentage displays will use 1 decimal place.

Summary statistics will be presented for continuous variables including number of participants (n), arithmetic mean, standard deviation, median, minimum and maximum. 95% confidence

intervals (CIs) for the arithmetic mean may also be included depending on the variable and where stated in the SAP. Geometric mean (geoMean), geometric coefficient of variation (geoCV) and 95% CI for the geoMean will also be presented in the summaries of UCB6114 concentration data. In all relevant outputs the 95% confidence limits will be restricted to the possible values that the variable can take.

When reporting descriptive statistics for data other than UCB6114 concentration data, the following rules will apply:

- n will be an integer;
- Mean (arithmetic and geometric), standard deviation, median and quartiles will use 1 decimal place more, or 1 significant figure more – depending on the reporting format of the original data – than the original data. Original data may be data as reported directly onto the eCRF or summary data based on data reported onto the eCRF (e.g. mean of triplicates or percentage change from Baseline);
- Confidence intervals will be presented to the same number of decimal places as the value around which the CI is constructed;
- Minimum and maximum will be reported using the same number of decimal places or significant figures as the original value;
- A minimum of 3 values are required to calculate summary statistics. If only 2 values are available, then these should be presented as the minimum and maximum with other summary statistics reported as missing ("– ");
- If no participants have data at a given timepoint, then only n=0 will be presented;
- Percentage change from Baseline values will be calculated and displayed to 1 decimal place in the listings. In the summaries, where applicable, the mean, standard deviation and median percentage change from Baseline values will be presented to 2 decimal places and the minimum and maximum values presented to 1 decimal place.

[figure not shown]
When reporting individual UCB6114 concentration data in listings and figures, and presenting summary statistics in tables, the following rules will apply:

- UCB6114 concentration data should be reported in the listings to the same level of precision as received from the bioanalytical laboratory;
- Missing data should be reported as 'NV' (no value) in the listings;
- Concentrations below the lower limit of quantification (LLOQ) should be reported as BLQ (below the limit of quantification) in the listings;
- BLQ values prior to C_{max} should be set to 0 for purposes of plotting a figure (to capture lag-time);
- Actual sampling times will be used in the spaghetti plots of individual PK concentrations over time, and nominal sampling times will be used in the summaries of geoMean concentrations over time;
- UCB6114 concentration data should be plotted on both linear and semi-logarithmic scales;

- To calculate summary statistics, BLQ values should be set to half the LLOQ value and missing values should be excluded;
- When the total number of BLQ and missing values exceeds one third of the total then only minimum and maximum should be reported for this timepoint. Other summary statistics should be reported as missing (“-“). The minimum should be reported as BLQ;
- When the mean value includes one or more replaced BLQ values then a footnote should be included to say “contains one or more BLQ values replaced by half the LLOQ value”;
- A minimum of 3 values are required to calculate summary statistics. If only 2 values are available, then these should be presented as the minimum and maximum with other summary statistics reported as missing (“- “);
- If no participants have data at a given timepoint, then only n=0 will be presented;
- Summary statistics for UCB6114 concentration data will be reported to the same level of precision as the individual data for the minimum and maximum, and to 1 additional decimal place or 1 additional significant figure – depending on the reporting format of the original data with a maximum of 3 significant figures - for the mean (arithmetic and geometric), median and standard deviation. The 95% CI for the geoMean will use the same number of decimal places or significant figures as the geoMean. It will be left blank if the geoCV is 0;
- Geometric coefficient of variation will be reported as a percentage to 1 decimal place. The geoCV will be calculated using the following formula where SD is the standard deviation from the log-transformed data:

$$GeoCV(\%) = \sqrt{\exp SD^2 - 1} \times 100$$

When reporting PK parameters in listings and figures, and presenting summary statistics in tables, the following rules will apply:

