4.2.1 Pharmacokinetics and pharmacodynamics

The reporting and handling of missing values and values that are BLQ in the TFLs is described in [Section 3.1](#). Zero values will be assumed at the predose timepoint on Day 1 of Cycle 1.

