4.2.2 Safety laboratory data

The rules for handling values that are BLQ in the safety laboratory data will be the same as those described for PK data in [Section 3.1](#). Any values above the limit of quantification (ALQ) will be assigned as the value of upper limit of quantification.

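### The one-third rule in SAP Section 3.1 orders the minimum to be shown as BLQ even where no value is BLQ, so missing samples alone can produce a false BLQ minimum

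*SAP*

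**What the plan says.** Section 3.1 of the Part B SAP lists the rules for summarising UCB6114 concentrations. Section 3.1 of the Part C SAP repeats them. Four bear on this point.

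- Substitution and exclusion: "To calculate summary statistics, BLQ values should be set to half the LLOQ value and missing values should be excluded".
- The one-third trigger, applied timepoint by timepoint: "When the total number of BLQ and missing values exceeds one third of the total then only minimum and maximum should be reported". The remaining statistics are blanked: "Other summary statistics should be reported as missing".
- The minimum once the trigger is met: "The minimum should be reported as BLQ".
- Sparse data, where summary statistics need at least 3 values: "If only 2 values are available, then these should be presented as the minimum and maximum with other summary statistics reported as missing".

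Two later sections extend the reach of these rules. Section 4.2.1, for PK and PD, reads: "The reporting and handling of missing values and values that are BLQ in the TFLs is described in" Section 3.1. Section 4.2.2, for safety laboratory data, points back to the same list: "The rules for handling values that are BLQ in the safety laboratory data will be the same as those described for PK data". The first names missing values as well as BLQ values. The second names only BLQ values.

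**The concern.** A BLQ result is a measurement: the sample was assayed and the concentration was too low to quantify. A missing sample says nothing about concentration. Section 3.1 keeps the two apart in the listings, where they carry different codes, and in the calculation of summary statistics. The one-third rule adds them together and then fixes the minimum as BLQ whichever of the two caused the trigger.

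If missing samples alone meet the trigger, the table reports a lowest concentration that was not observed. The table concerned carries the secondary endpoint, UCB6114 concentration by scheduled assessment, in dose levels that Section 2.3 sets at 3 to 9 evaluable participants. In groups that small, two to four absent samples are enough. A reader of the summary table alone would take the entry to mean that at least one participant had unquantifiable drug at that visit.

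**Working it through.** The plan derives no figure from this rule, so there is none to reproduce. The check applies the rule as written.

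**Inputs.** Group size: 3 to 9 evaluable participants per dose level (Section 2.3). Trigger, blanking, BLQ minimum and 3-value floor: Section 3.1. Assumption: the total includes the missing samples. The SAP does not define it, but otherwise missing values could not be a share of it.

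**Formula.** Let N be the total, m the number missing and b the number BLQ. The rule fires when (b + m)/N > 1/3. With b = 0 it fires when m > N/3.

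**Smallest m that fires the rule with no BLQ value:**

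| N | m | m/N | Quantifiable values left | Minimum printed |
|---|---|---|---|---|
| 3 | 2 | 66.7% | 1 | BLQ |
| 4 | 2 | 50.0% | 2 | BLQ |
| 5 | 2 | 40.0% | 3 | BLQ |
| 6 | 3 | 50.0% | 3 | BLQ |
| 7 | 3 | 42.9% | 4 | BLQ |
| 8 | 3 | 37.5% | 5 | BLQ |
| 9 | 4 | 44.4% | 5 | BLQ |

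In every row the printed minimum is false. From N = 5 upward the 3-value floor is met, so the mean, SD, median and geometric mean are blanked by the one-third rule alone. At N = 3 and 4 the floor would remove them anyway, and only the false minimum is added.

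**Conflict inside the list.** Take N = 4, m = 2, b = 0. The sparse-data bullet shows the two observed values as minimum and maximum. The one-third rule also applies, since 2/4 = 50% > 33.3%, and shows BLQ as the minimum. A programmer cannot satisfy both. The same clash arises whenever exactly two quantifiable values remain and the trigger is met, for example 3 missing of 5 or 4 missing of 6.

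**How often.** The SAP states no missing rate. Assume, for illustration only, that samples are missing independently with probability q and that none is BLQ. The chance that the rule fires with at least one value observed is the sum over m > N/3, m < N, of C(N, m) q^m (1 − q)^(N − m):

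| q | N = 5 | N = 6 | N = 9 |
|---|---|---|---|
| 10% | 8.1% | 1.6% | 0.8% |
| 20% | 26.2% | 9.9% | 8.6% |
| 30% | 46.9% | 25.5% | 27.0% |
| 40% | 65.3% | 45.2% | 51.7% |

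The result runs from rare to routine over plausible values of q. It also depends on the undefined total. If participants who have left treatment count as missing, the effective q rises in later cycles; if only expected samples count, it stays lower.

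**The case against.** **Suppressing the mean is a legitimate choice.** Blanking the mean and geometric mean when more than a third of a timepoint is absent or unquantifiable is a cautious display rule for groups this small. It contradicts nothing: a missing value can be left out of a calculation and still count in deciding whether to show the result, and the 3-value floor does not exclude a second criterion. This stands. It does not defend printing BLQ where no result is BLQ.

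**The laboratory tables.** A reader might infer that a neutrophil or platelet minimum would also be printed as BLQ when every value is quantifiable. The text does not clearly lead there. Section 4.2.2 imports only the handling of values that are BLQ, whereas Section 4.2.1 names missing values too. Section 3.1 also has a separate list for data other than UCB6114 concentrations, with its own 3-value floor and no one-third rule. Where no laboratory value is BLQ, the more natural reading is that this second list governs. Section 4.2.2 is ambiguous here, not plainly wrong.

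**The true values remain visible.** The maximum is still shown, the individual concentrations are listed with missing and BLQ coded differently, and spaghetti plots are planned. A careful reader could detect the false entry. This limits the harm but does not make the summary correct.

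**Unseen text might qualify the rule.** Sections 9.1.1 and 9.1.2 are redacted, and reporting also follows a sponsor conventions document that is not shown. Either could hold a qualifier, but the visible rule has none and cannot be assumed repaired elsewhere.

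**Conclusion.** The rule is wrong as written in one respect: it orders a BLQ minimum without requiring a BLQ value. For UCB6114 concentrations, and for PD data through Section 4.2.1, any timepoint with more than one third of values missing and none BLQ would show a false minimum. At dose levels of 5 to 9 participants this takes 2 to 4 missing samples. Where two quantifiable values remain, the rule also contradicts its neighbour in the same list. Both SAPs are affected.

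The consequence is confined to descriptive reporting. A reader might infer that dose escalation is affected, or that valid data are discarded. Neither follows: escalation rests on DLTs, and the individual values stay in the listings. The frequency is unknown, because the missing rate and the meaning of the total are both unstated. The conclusion rests on the total including missing samples and on no qualifier sitting in the redacted or unseen text.

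**What to change.** In Section 3.1 of both SAPs, replace the sentence on the minimum with: *The minimum is reported as BLQ only if at least one value at that timepoint is BLQ; otherwise the observed minimum is reported.* This also removes the conflict with the two-value bullet when neither value is BLQ. State in the same place whether the total means expected samples or all participants in the group.

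In Section 4.2.2 of both SAPs, add that the rule applies to a laboratory parameter only where a BLQ value exists at that timepoint.

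Optionally, base the one-third trigger on BLQ values among non-missing values and leave missing values to the 3-value floor. This is a display choice, not a correction.

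- With 9 samples, 4 missing and none BLQ, the share becomes 0/5 = 0% and the statistics are shown.
- With 9 samples, 3 missing and 1 BLQ, it becomes 1/6 = 16.7% and they are shown.
- True BLQ cases stay blanked: 4 BLQ of 9 is 44.4%, and 3 BLQ of 7 non-missing is 42.9%.
- The price is that some thin summaries appear. With 9 samples, 6 missing and 1 BLQ, the share is 1/3, which does not exceed one third, so a geometric mean would rest on two measurements and one substituted half-LLOQ value.

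The main change costs one sentence in each SAP and one condition in the summary macro.
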